APPENDIX A. SCHEDULE OF PROCEDURES AND ASSESSMENTS

Study Activity	Screen ^c	Day 1 ^c	Day 14 ^g	Day 29	Day 57 ^g	Day 85/ End of study ^{a, d}	Specimen	
Demographics	X							
Full Physical Exam,	X							
Focused Physical Exam,		X				X		
Medical History to include: 
 • Duration of ADT • Extent of cancer • Personal history of diabetes mellitus • Current medications 	X	X						
Interim Medical History		X				X		
Anthropometric Measurements (height, weight)	X	X				X		
CBCD	X	X				X		
CMP (fasting) ^g	X	X				X		
Phosphorus	X	X				X		
PSA	X	X				X		
Assessment of toxicity		X	X ^g	X ^g	X ^g	X		
testosterone	X	X				X		
Chitosan			X-----X					
Drug diary review ^e						X		
Informed consent	X							
Insulin Resistance (HOMA-IR)		X ^f				X	Plasma ^b	
CRP, AGE species and precursors		X ^f				X	Serum ^b	
RedOx status (ORP, reduced glutathione)		X ^f				X	Plasma ^b	
RAGE, TLR expression, signaling		X ^f				X	Whole blood ^b	
Microbiome profiling		X ^f				X	Stool	
AGE species		X ^f				X	Urine ⁱ	
Tissue AGE level by autofluorescence		X				X		
Food Recall Dietary AGE content ^h		X ^f				X		
QOL (FACT-P and AUA)		X ^f				X		

- All days are +/- 5 days
- 2x7mL EDTA blood (=plasma), 2x7mL clot tube (=serum), 1x7mL sodium heparin tube (=whole blood).
- Screening assessments to be done within 28 days of registration. Screening assessments may be used for the day 1 assessments if they were completed within 28 days of day 1. The CMP used for eligibility confirmation does not have to be fasting, but a fasting CMP will need to be collected prior to day 1 drug administration. Fasting is defined as nothing containing calories since the previous midnight.
- If the subject goes off study less than 2 weeks after start of dosing, "end of study" labs and questionnaires will not be done.
- The drug diary will be given to each subject for completion during the study.
- Research procedures (excluding informed consent) may be done at any point after informed consent and prior to first dose of drug (on day 1). Research blood, urine and stool samples will be taken to the participating research lab(s) for processing.

NCT # NCT03712371

CTO # 102928

Version Date: 09/09/2020

- g) On day 14, day 29, and day 57 (+/- 5 days), compliance and adverse events will be assessed via phone using the phone contact guide in appendix D.
- h) Food recall using the NCI quick food scan and the NIH's "Eating at America's Table Study" Quick food scan.
- i) 10mL of urine collected in a sterile cup such as those used for clinical urine specimens

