4.4 Discontinuation of Therapy

Participation in this study should be discontinued for any of the following reasons:

- Change in anti-cancer therapy
- Procedures requiring general anesthesia.
- Development of any medical condition that, in the opinion of the treating physician, requires discontinuation of the study intervention
- Withdrawal of consent by the subject
- Evidence of allergic reaction to any component of the treatment regimen
- Any grade 3-4 hematologic or non-hematologic toxicity (other than in 4.5) that does not resolve, with drug discontinuation, to grade 1 or less in 14 days.

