7.4 Withdrawal of subjects

Subjects can withdrawal from the study at any time without if affecting their regular care. The subject can be removed from study at any time if it is determined it is not in the subject's best interest to remain on the trial, the subject is non-compliant, or if the study is closed.

If the subject withdraws or is withdrawn from the study, the study team will stop collecting new information and specimen from the subject, but information and specimens already collected may still be used in the data analysis.

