AEs should be followed to resolution or stabilization, and reported as SAEs if they become serious. This also applies to subjects experiencing AEs that cause interruption or discontinuation of study

drugs, or those experiencing AEs that are present at the end of their participation in the study; such subjects should receive post-treatment follow-up as appropriate. All SAEs must be collected which occur within 30 days of discontinuation of dosing or completion of the patient's participation in the study if the last scheduled visit occurs at a later time.

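### Appendix A footnote d waives end-of-study labs without separating safety labs from research samples, so a subject off study within 2 weeks has no scheduled post-dose safety laboratory value

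*Combined protocol and SAP*

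**What the plan says.** The Appendix A grid marks CBCD, CMP and phosphorus in three columns: Screen, Day 1 and Day 85/End of study. The first two are baseline. The footnotes say "Screening assessments may be used for the day 1 assessments if they were completed within 28 days of day 1", and that "a fasting CMP will need to be collected prior to day 1 drug administration". Between Day 1 and the final column there are only telephone contacts: "On day 14, day 29, and day 57 (+/- 5 days), compliance and adverse events will be assessed via phone".

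Footnote d is attached to the Day 85/End of study column and reads "If the subject goes off study less than 2 weeks after start of dosing, 'end of study' labs and questionnaires will not be done". It makes no exception by reason for leaving and does not say which labs it means. The column holds both kinds: the three safety panels, and research assays such as AGE species, redox status and receptor signaling.

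Other sections bear on the same subjects:

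- **Section 4.4** opens "Participation in this study should be discontinued for any of the following reasons". Its list includes "Evidence of allergic reaction to any component of the treatment regimen" and any medical condition that the treating physician judges to require stopping. These are exits from the study, so footnote d applies if they occur early enough.
- **Section 5.2** lists CBCD and CMP among the clinical assessments at Day 85/End of study, as items separate from the research samples and with no 2-week exemption. Phosphorus is neither in that list nor among the CMP components it names.
- **Section 7.4** provides that once a subject withdraws or is withdrawn, "the study team will stop collecting new information and specimen from the subject".
- **Section 8.2** has AEs followed to resolution or stabilization. It adds "This also applies to subjects experiencing AEs that cause interruption or discontinuation of study" drugs, leaves the follow-up to what is appropriate, and collects SAEs for 30 days after dosing stops.
- **Section 10.1** counts DLTs only in the first 28 days and makes grade 3 or higher hypophosphatemia a DLT, with no attribution or duration condition.

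**The concern.** Skipping research assays and questionnaires after a very short exposure is reasonable. The difficulty is that the same sentence, taken literally, also removes the only scheduled post-dose safety draw.

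The AE follow-up in section 8.2 starts from an event that someone has recognised. It schedules no test that would find a silent laboratory abnormality, and hypophosphatemia can be one. The protocol itself gives a reason to look: section 1.6.2 says chitosan can bind phosphorus, and section 1.6.4 reports lower serum phosphorus in rats at the 9% dietary level.

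The primary objective is the MTD, and escalation turns on cohorts of 3 or 6. Section 10.1 does not say whether a subject who leaves within 2 weeks is evaluable for DLT or is replaced. A subject with no post-dose phosphorus value could therefore be counted as free of DLT.

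**Working it through.** **Step 1. Count the scheduled post-dose safety draws (CBCD, CMP, phosphorus) from the Appendix A grid and footnotes.**

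| Subject | Day 14 / 29 / 57 | End of study or Day 85 | Total |
|---|---|---|---|
| Off study before 2 weeks | phone only | waived by footnote d | 0 |
| Off study after 2 weeks, before Day 85 | phone only | 1 | 1 |
| Completes Day 85 | phone only | 1 | 1 |

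Exits covered by footnote d occur in under 14 days, so all fall inside the 28-day DLT window.

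**Step 2. Is the waiver limited to research labs?** Footnote d says labs without qualification, and the column it qualifies contains CBCD, CMP and phosphorus. Footnote f, in the same table, uses the word research when it means research samples. Section 5.2 points the other way for CBCD and CMP, since it carries no exemption. It does not help for phosphorus, which it does not list. The text therefore permits both readings for two panels and gives only one source for the third.

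**Step 3. How many subjects?** The plan states no early drop-out rate, so there is no figure to reproduce. The range below is assumed, using two rows of Table 1 (section 1.6.4) and the maximum accrual of 54 (section 10.2).

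- *Lower assumption:* 7/65 drop-outs on chitosan over 3 months, at a constant rate, with 3 months taken as 90 days. 7/65 = 10.8%, and 10.8% × 14/90 ≈ 1.7% by day 14.
- *Upper assumption:* 2/15 withdrawals on chitosan over 28 days, all falling before day 14. 2/15 = 13.3%.
- *Between them:* half of the 2/15 falling before day 14, which is 6.7%.

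Expected number affected = 54 × rate. Chance that a 3-patient cohort contains at least one = 1 − (1 − rate)³, taking subjects as independent with a common rate.

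| Assumed rate by day 14 | Expected of 54 | At least one in a cohort of 3 |
|---|---|---|
| 1.7% | 54 × 0.017 = 0.9 | 1 − 0.983³ = 5% |
| 6.7% | 54 × 0.067 = 3.6 | 1 − 0.933³ = 19% |
| 13.3% | 54 × 0.133 = 7.2 | 1 − 0.867³ = 35% |

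The range is about 1 to 7 subjects, and 5% to 35% of 3-patient cohorts. The upper end is a bound more than an expectation, because it needs every 28-day withdrawal to fall in the first half of the period.

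**The case against.** The strongest objection is that the DLT problem is not footnote d's doing. Subjects who stay on study have no phosphorus scheduled inside the 28-day window either, because Days 14, 29 and 57 are telephone contacts. Their laboratory DLT status inside the window is just as unmeasured, and a draw at an exit on, say, day 5 would not settle 28-day status. This stands: the wider gap is larger, and footnote d is one part of it. What remains is that other subjects get at least one scheduled post-dose value and these get none.

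Second, a reader might infer that subjects removed for an allergic reaction leave without safety follow-up. The documents do not support that. Such a subject has a recognised AE, which section 8.2 follows, with unscheduled tests possible. Footnote d waives labs and questionnaires, not the focused exam or the toxicity assessment, and a removal after 2 weeks keeps the labs. The gap is confined to scheduled tests and to abnormalities that no one has reason to suspect.

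Third, a reader might infer that early leavers are those the drug has harmed. The Table 1 row behind the upper assumption reports 2/15 withdrawals on placebo as well, with the dose not stated and no reasons given. The 7/65 row has 5/65 on placebo, and a 21-day row reports that no subject discontinued. Drug-related exit is possible for removals under section 4.4, but these figures do not show it.

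Fourth, one might say that laboratory summaries would be biased toward those who tolerated treatment. Section 10.2 specifies no CBCD, CMP or phosphorus summary, so there is no planned analysis to bias.

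**Conclusion.** The point holds in a limited form. As written, footnote d leaves a subject who is off study less than 2 weeks after the first dose with no scheduled post-dose CBCD, CMP or phosphorus. This sits badly with a laboratory-defined DLT and with section 5.2, which lists CBCD and CMP at End of study without the exemption.

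The count of draws follows directly from the grid. The size, about 1 to 7 of 54 subjects and 5% to 35% of 3-patient cohorts, rests on drop-out rates borrowed from other chitosan studies and on assumptions about timing within them; the lower end needs the less extreme assumption.

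The documents do not support reading this as an absence of safety follow-up, as evidence of drug-related drop-out, or as the main cause of unmeasured laboratory DLTs. It is a drafting gap with a modest effect on safety data, and it is worth correcting because correction is cheap.

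**What to change.** Reword footnote d so that it names research samples and questionnaires only and no longer waives the scheduled safety labs. Then reconcile it with three other places:

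- **Section 5.2**, so that the End of study list and the grid agree, including on phosphorus, which only the grid contains.
- **Section 7.4**, which stops new information and specimens once a subject withdraws or is withdrawn. Amending footnote d alone would leave a contradiction.
- **Section 8.2**, so that the discretionary follow-up of AEs causing discontinuation and the scheduled exit assessment fit together.

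Which safety tests are done at early exit, and when, is for the sponsor to decide.

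The cost is a one-sentence amendment with its cross-references, and one routine blood draw in a few subjects, in a column whose focused exam and toxicity assessment footnote d does not waive. The change does not repair the wider gap that no phosphorus is scheduled inside the 28-day DLT window for subjects who stay on study, which needs separate attention.

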4.2 Chitosan administration

Subjects will be enrolled sequentially into four cohorts; the starting dose level is cohort 1. These cohorts will take chitosan as described in Table 2. Three patients will be enrolled into cohort 1, and no patients will be enrolled into the next cohort until the final patient in cohort 1 will have completed 28 days of treatment.

Chitosan will be taken up to 30 minutes before, or during, the middle and evening meals (BID dosing) or the largest meal of the day (Q day dosing). Chitosan will not be taken with breakfast, and the subjects should endeavor to take any chronic medicines before or with breakfast to minimize the chance of absorption of pharmaceuticals to chitosan. Any pharmaceuticals should be taken at least 1 hour before or 2 hours after chitosan. Any chitosan doses lost through vomiting will not be made up.

Cohort	Chitosan
-1	500mg Q day
1	500mg BID
2	1000mg BID
3	1500mg BID
4	2000mg BID

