5 SCHEDULE OF INTERVENTIONS AND ASSESSMENTS

5.1 General Considerations

- Informed consent must be signed prior to any study-specific assessments being done
- Screening assessments may be done up to 28 days prior to registration. Screening assessments completed within 28 days of day 1 do not have to be repeated.
- Day 85 or End of Study Assessments may be done +/- 3 days.
- All research and clinical blood samples must be collected while the subject is fasting.

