5.2 Assessments and Procedures

The following clinical assessments are made at the time subjects are screened for the trial. Some of these may need to be repeated prior to day 1; see Appendix A for more details regarding the schedule of procedures and assessments.

- A full medical history and physical examination to review patient medical history, medication list, overall health and any side effects they may be experiencing. Medical history will include:
 - Extent of cancer to include metastatic disease
 - Concomitant medications
 - current ADT therapy
- Height, weight
- CBCD
- CMP (sodium, potassium, chloride, bicarbonate, BUN, creatinine, glucose, albumin, alkaline phosphatase, AST, ALT, calcium)
- PSA, testosterone
- Research blood, urine, and stool samples as outlined (see Appendix A)
- 24hr food intake recall questionnaire
- Quality of life questionnaires (FACT-P and AUA; see Appendices B, C)
- Measurement of tissue AGE level by skin autofluorescence using the AGE Reader device.

On day 29 of the study, a phone call will be made to the patient to assess any possible adverse events (AEs).

The following clinical assessments are made on day 85/End of study

- Interim medical history and focused physical exam to review:
 - Changes to the patient's medical history,
 - Changes to ADT

- Changes to familial history of diabetes
- Change to medication list
- Overall health and any side effects they may be experiencing.
- Height, weight
- CBCD
- CMP (sodium, potassium, chloride, bicarbonate, BUN, creatinine, glucose, albumin, alkaline phosphatase, AST, ALT, calcium)
- PSA
- Research blood and urine samples as outlined (see Appendix A)
- 24hr food intake recall questionnaire
- Measurement of tissue AGE level by skin autofluorescence using the AGE Reader device.
- Day 85: Quality of life questionnaires (FACT-P and AUA; see Appendices B, C)

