10 STATISTICAL METHODS AND POWER ANALYSIS

10.1 Escalation Design

The investigators will use a 3+3 design for assignment to cohorts. The cohorts are shown in Table 3. An initial 3 subjects will be enrolled at dose level 1. Dose-limiting toxicities (DLT) will be defined only in the first 28 days of therapy. If there are no DLTs after the final patient has been treated for 28 days, then the next cohort will be enrolled in dose level 2, and so forth. If a DLT occurs, then 3 more subjects will be enrolled into that cohort. If two DLTs occur in the first 3 patients in a dose level, then dose will be de-escalated and 3 additional patients will be enrolled in the lower dose

Dose Level	Chitosan	number
-1	500mg QD	3 (+3)
1	500mg BID	3 (+3)
2	1000mg BID	3 (+3)
3	1500mg BID	3 (+3)
4	2000mg BID	3 (+3) +30

level unless 6 have already been treated at that dose level. The MTD will be defined as the dose at which no more than 1 out of 6 subjects experiences a DLT.

Definition of DLT:

- Grade 3 or higher hypophosphatemia
- Grade 3 or higher of any of the following toxicities, that the investigator deems related to chitosan, that do not improve or resolve within 7 days of onset: flatulence, increased stool bulkiness, bloating, nausea, heartburn

10.2 Expansion Cohort Design and Statistical Analysis.

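### The next cohort may open on day 29 before a late-onset GI event has run its 7-day DLT test, and the end-of-window toxicity call may fall before day 28

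*Combined protocol and SAP*

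**What the plan says.** Four provisions bear on when a cohort's DLT count is complete.

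- **Window.** Section 10.1: "Dose-limiting toxicities (DLT) will be defined only in the first 28 days of therapy".
- **Release of the next cohort.** Section 10.1: "If there are no DLTs after the final patient has been treated for 28 days, then the next cohort will be enrolled". Section 4.2 sets the same minimum, but for the first cohort only: "no patients will be enrolled into the next cohort until the final patient in cohort 1 will have completed 28 days of treatment".
- **GI DLT definition.** Section 10.1 lists five GI toxicities. At grade 3 or higher, and judged related to chitosan, they count as DLTs if they are events "that do not improve or resolve within 7 days of onset". Hypophosphatemia of grade 3 or higher counts without any such waiting period.
- **Toxicity contacts.** Appendix A, footnote g: "On day 14, day 29, and day 57 (+/- 5 days), compliance and adverse events will be assessed via phone". Section 5.2 mentions one call, with no window: "On day 29 of the study, a phone call will be made to the patient to assess any possible adverse events". Appendix A shows no clinic visit between day 1 and day 85, and marks the drug diary review only at day 85.

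**The concern.** The MTD is the primary objective (Section 2.2), and the DLT count alone decides it. Two timing rules can make that count incomplete when escalation is decided.

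First, the release rule runs on 28 days of treatment, while the GI definition needs up to 7 days after onset. An event that begins near the end of the window is neither a DLT nor a non-DLT when the next cohort may start.

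Second, the only scheduled toxicity contact near the end of the window may take place before the window ends.

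Both gaps err in one direction: DLTs are missed or recognised late. The consequence would be patients entering a higher dose level on a count that later turns out too low, or an MTD declared on such a count.

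**Working it through.** The plan gives no figure for this point, so there is none to reproduce. The check is day arithmetic, followed by an illustration.

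**Inputs.** DLT window: days 1 to 28 (10.1). Earliest release: day 29 of the final patient (10.1). Time to classify a GI event: 7 days from onset (10.1). Call windows (Appendix A, footnote g): 14 ± 5 = days 9 to 19; 29 ± 5 = days 24 to 34; 57 ± 5 = days 52 to 62.

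**Step 1: status at release.** The last onset day that can be classified by day 29 is 29 − 7 = 22. Onsets on days 23 to 28 are still open: 6 of 28 days, or 21%. If the onset day counts as day 1 of the 7, the last classifiable onset is day 23 and 5 of 28 days stay open. This holds whatever the date of the call. An onset on day 28 is classified on day 28 + 7 = 35 (day 34 on the other count), 6 (or 5) days after the earliest release.

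**Step 2: the other reading of the window.** If the 7 days must finish by day 28, the last onset that can count is day 28 − 7 = 21 (day 22 on the other count). Status is then complete at release, but the GI window is about 21 days rather than 28. Section 10.1 does not say which reading applies.

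**Step 3: contact.** A call on day 24 leaves days 25 to 28 (4 days) with no scheduled contact before days 52 to 62. A call on day 34 covers the window, but comes 5 days after the cohort may have opened.

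**Step 4: illustration.** Take a dose to pass if 0 of 3 patients have a DLT, or 1 of 3 and then 0 of 3; this follows from the MTD rule of at most 1 in 6. With P0 and P1 the chances of 0 and 1 recognised DLTs in three patients, pass = P0 + P1 × P0. Assume a true DLT rate of 0.30, onset uniform over 28 days, every DLT a GI event, and every pending event scored as no DLT. An affected patient's recognised rate is 0.30 × 22/28 = 0.236.

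| Patients affected | P0 | P1 | Pass |
|---|---|---|---|
| None | 0.70³ = 0.343 | 3 × 0.30 × 0.70² = 0.441 | 0.49 |
| Last of each three | 0.70² × 0.764 = 0.375 | 2 × 0.30 × 0.70 × 0.764 + 0.70² × 0.236 = 0.437 | 0.54 |
| All | 0.764³ = 0.446 | 3 × 0.236 × 0.764² = 0.413 | 0.63 |

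The middle row assumes that the other two patients started about a week or more earlier, so that their 7-day periods are over. At a true rate of 0.10 the first and last rows become 0.91 and 0.94.

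**The case against.** The strongest reply is that Section 10.1 is conditional and sets a minimum. It permits release after 28 days without DLTs, and a careful investigator who knows of an ongoing grade 3 event can wait. Known events are also tracked. Section 8.1 has adverse events recorded prospectively and allows spontaneous reports, Section 8.2 has them followed until they resolve or stabilise, and Section 4.4 needs a judgement on resolution over 14 days. Published experience summarised in Section 1.6.4 shows no grade 3 or 4 events in 371 patients, so a 30% rate is not an expectation.

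Much of this stands, and it limits the size of the problem. It does not remove it: the protocol allows waiting but nowhere requires it, and spontaneous reports may catch only some events. The 24-hour reporting duty covers serious events, and a grade 3 GI event need not be serious.

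Three stronger readings are tempting and are not supported.

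- A reader might infer that a day-24 call lets the cohort open on day 24. It does not; 28 days of treatment are still required.
- A reader might infer that the day-29 call formally closes the DLT window and that days 25 to 28 go unobserved after an early call. No section ties DLT status or release to the call. What is missing is a scheduled contact.
- A reader might count 11 of 28 onset days (39%) as lost after a day-24 call, because 24 − 7 = 17 leaves days 18 to 28. But onsets on days 18 to 22 precede that call and reach their seventh day by days 25 to 29, in time for the release decision if followed as Section 8.2 requires. At release, 6 of 28 is the right count.

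**Conclusion.** The concern holds in limited form. Followed exactly, the 28-day release rule and the ± 5 day call window can open a cohort while the DLT status of the current one is incomplete. The certain part is textual: GI onsets on days 23 to 28 (24 to 28 if the onset day counts as day 1) cannot be classified by day 29, no provision holds the cohort for them, and the call meant for day 29 may precede the end of the window. If the 7 days must finish within day 28, the defect is instead an unstated shortening of the GI window to about 21 days.

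The operating-characteristic figures are illustrative. The 0.54 and 0.63 against 0.49 rest on a 30% rate, uniform onset, all DLTs being GI, and pending events scored as no DLT; 0.63 is a worst case. At low DLT rates the effect is small. The amendment is worth making because it is cheap and protects the primary endpoint.

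**What to change.** 1. In Appendix A, footnote g, make the window of the day-29 call one-sided, so that the call is not made before day 29. Bring Section 5.2 into line.
2. In Section 10.1, for every cohort, allow the next cohort to open only when two conditions are met. Each patient's end-of-window toxicity contact has been made, and any listed grade 3 or higher event with onset in days 1 to 28 has been followed until its 7-day criterion is met or not met. State that onset within 28 days is what counts, and whether the onset day is day 1 of the 7. Extend the Section 4.2 wording beyond cohort 1.

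Requiring the call before release matters: a one-sided window alone would still let a cohort open on day 29 with the call to follow.

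**Cost.** Protocol wording only. Expect a few days' delay per cohort if the call falls late in its window, and about a week if an event is pending.

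Two mismatches are separate editorial points to reconcile at the same time: one toxicity call in Section 5.2 against three in Appendix A, and the day-85 window of ± 3 days in Section 5.1 against ± 5 in Appendix A. Neither affects the DLT count.
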